2. PUCAI

Pediatric Ulcerative Colitis Activity Index (PUCAI) is calculated as the sum of six subscores [each being a 2 day average, see above] of PUCAI (abdominal pain [no pain = 0, pain can be ignored = 5, pain cannot be ignored = 10], rectal bleeding [none = 0, small amount with < 50% of stools = 10, small amount with most stools = 20, large amount with > 50% of stool content = 30], stool consistency of most stools [formed = 0, partially formed = 5, completely unformed = 10], number of stools per 24 hours [0 to 2 = 0, 3 to 5 = 5, 6 to 8 = 10, > 8 = 15], nocturnal stools [no = 0, yes = 10], activity level [no limitation = 0, occasionally limited = 5, severe restriction = 10]) with maximum total score 85. Higher scores represent more severe disease.

- PUCAI remission is defined as PUCAI < 10.
- PUCAI response is defined as a decrease in PUCAI ≥ 20 points from Study M11-290-Baseline.

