The PUCAI score will be assessed using subject-reported symptoms and activity level. The answers should reflect symptoms and activity level during the previous 24 hours. The PUCAI scores of the last 2 days prior to each study visit will be averaged and used for the PUCAI scores for each study visit. The total PUCAI score will be rounded up to the next 5-point interval as applicable. In order to account for unavailable or excluded diary entries as per the provisions given below diary entries for the PUCAI score of the most recent 2 days within 10 days prior to each study visit will be used.

Diary entries of the following days should not be included in the 2 days prior to the visit that are evaluated for the PUCAI score: (1) the day the subject received medication for bowel preparation prior to endoscopy, (2) the day the subject underwent an endoscopy, and (3) 2 days following the endoscopy. Earlier diary entries will be used accordingly in order to provide the most recent data for 2 days prior to the respective study visit.

The subscore for the number of stools per 24 hours during days which a subject received anti-diarrheal medication will be scored as 15.

Mayo Score

All subjects will be provided with a Subject Diary at the Baseline Visit where they will record ulcerative colitis related symptoms. The Partial Mayo Score will be calculated from the subject diary at each visit beginning at Baseline. The average entry from the 5 days prior to each study visit will be used for each subject-reported subscore. In addition to the physical examination, the investigator should use the subject-reported

subscores of abdominal discomfort and functional assessment to determine the physician's global assessment subscore.

Normal number of bowel movement is the number of stools per day (24 hours) that is typical for the subject when having active UC but not experiencing a flare. Each subject serves as his or her own control to establish the degree of abnormality of the stool frequency.

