For composite scores which consist of several component subscores, components will be imputed first and the composite score will be calculated based on imputed component subscores. Only if composite score still can't be calculated after imputing component subscores, then the previous composite score will be carried forward.

[figure not shown]

Missing Items on Questionnaire Scales:

Mayo scores (and alternative composite scores) can only be calculated if all subscores included are collected. If one or more subscores are missing, the score will be considered missing. No imputations will be made. The symptoms of stool frequency and rectal bleeding are scored as a 5 day average of daily values from up to 14 days preceding the visit, rounded to one decimal place. The most recent consecutive days will be used. If consecutive days are not available, then non-consecutive days can be used. Diary entries for stool frequency and rectal bleeding should not be included in the 5 days prior to the visit that are evaluated for these subscores for the following days: (1) the day the subject received medication for bowel preparation prior to endoscopy, (2) the day the subject underwent an endoscopy, and (3) 2 days following the endoscopy. Earlier diary entries will be used accordingly in order to provide the most recent data for 5 days prior to the respective study visit. If less than 3 days of diary data are available, stool frequency and rectal bleeding subscores will be considered missing.

[figure not shown]
When calculating **PUCAI**, if more than 3 subscores are missing then PUCAI will be considered missing. Otherwise, for missing subscores, the last available post-baseline value for the respective subscore will be carried forward to compute the total PUCAI score. The subscores of abdominal pain, rectal bleeding, stool consistency, number of stools per 24 hours, nocturnal stools and activity level are scored as a 2 day average, rounded to one decimal place. The most recent consecutive days will be used. If consecutive days are not available, then non-consecutive days can be used.

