Partial Study Dates: If the day and/or month are missing, the following conventions will be used to impute the missing visit (or assessment) dates other than the dosing dates:

- 01 for missing start day,
- End of month for missing end day,
- January 1st will be used for a missing start month,
- December 31st for missing end month.

[figure not shown]
In case of partially missing AE start and stop dates, the dates will be imputed by comparing to first dose date of study medication so that the corresponding AEs will be made treatment-emergent whenever possible.

In case of missing or partially missing study drug dosing dates, the dates will not be imputed. Subjects will be considered as not receiving dose on that date.

Rounding

Rounding will be performed only for presentation of results. No rounding will be performed before or during analyses/calculations. The ROUND function of SAS will be used to round results for presentation.

The mean and median will be rounded for presentation to one decimal more than the data were entered into the database. For example, mean systolic blood pressure will be presented to one decimal place (125.2 mmHg) when it is recorded to integer level in the database (110 mmHg). The standard deviation will be rounded to two decimal places more than the data were entered into the database (e.g., 25.31 mmHg for systolic blood pressure). The minimum and maximum values will be presented as entered into the database.

Probabilities will be rounded to three decimal places before assignment of statistical significance and will be presented in rounded format. Probabilities that round to zero or are reported by SAS as zero will be presented as '< 0.001.'

Percentages will be rounded for presentation to one decimal place; e.g., the proportion 0.1244 will be reported in percent as 12.4%.

Score Definitions

1. Mayo Score and Component Scores

 Table 1.
 Definition of Mayo Score and Component Scores

Term	Definition	
Mayo Score	Composite score of UC disease activity based on the subscores of stool frequency $(0-3)$, rectal bleeding $(0-3)$, physician's global assessment $(0-3)$ and endoscopic subscore $(0-3)$. This score ranges from $0-12$ points with higher scores representing more severe disease.	

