7.1 Demographic and Baseline Characteristics

Demographics and baseline disease characteristics and UC disease history values will be summarized using descriptive statistics. For the following characteristics marked by '#' the source data from Study M11-290 should be used for analyses (although some of the

items may also have been transferred from Study M11-290 into the Study M10-870 database).

Demographics and baseline characteristics:

• Subject demographics

- Sex# (female, male)
- Age [years] {using birth date#}
- Age categories ($< 13 \text{ years}, \ge 13 \text{ years}$)
- o Race# (White, Black, Asian, American Indian/Alaska Native, and Other)
- Ethnicity# (Hispanic or Latino, Japanese, no ethnicity)
- o Geographic region# (North America, Western Europe, Eastern Europe)
- Body Weight# [kg]
- o Body Weight categories ($< 40, 40 < 60, \ge 60 \text{ kg}$)
- Height# [cm]
- \circ BMI [kg/m²]
- Tobacco/Nicotine Use#* (current user, former user, never, or unknown)
- Alcohol Use#* (current user, former user, never, or unknown)
- * Data from Study M11-290-Baseline, to be clarified in a footnote to the table.

• PPD skin test/QuantiFERON®-TB Gold test/TB prophylaxis#

- Tuberculin PPD skin test (negative, positive), positive defined as ≥ 5 mm
- QuantiFERON-TB Gold test (negative, positive, indeterminate)
- Combined result of Tuberculin PPD skin test and QuantiFERON-TB Gold test
- Enrollment under TB prophylaxis (yes, no)

• Disease characteristics at Baseline

- Duration of UC
 - In months: (Baseline date date of diagnosis of UC# + 1)/(365.25/12)
 - In years: (Baseline date date of diagnosis of UC# + 1)/365.25
- Site of UC# (Left sided UC vs. Extensive UC/pancolitis)

[figure not shown]
- Mayo Score#
- Mayo Score at Study M11-290-Baseline#
- Partial Mayo Score# (PMS)
- o PMS at Study M11-290-Baseline#
- Endoscopy Subscore#
- Rectal Bleeding Subscore#
- Physician's Global Assessment (PGA) Subscore#
- Stool Frequency Subscore#
- Number of stools in the last 24 hours prior to baseline# (i.e., last non-missing value $-1 \le Rx$ Day ≤ 1)
- o PUCAI#
- o PUCAI at Study M11-290-Baseline#
- IMPACT III total score and subscores#
- WPAI# (Absenteeism, Presenteeism, Work Impairment, Activity Impairment)
- o hs-CRP# [mg/L]

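### SAP 6.0 has two scoring rules to correct: the PUCAI total omits the protocol's round-up to a multiple of 5, and the z score for height has a height-velocity formula paired with a stature-for-age table

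*SAP*

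**What the plan says.** **PUCAI.** Protocol 5.3.1.1 averages the PUCAI scores of the last two days before a visit and then adds: "The total PUCAI score will be rounded up to the next 5-point interval as applicable". The SAP has no such step. Under Score Definitions in SAP 6.0 the total "is calculated as the sum of six subscores [each being a 2 day average, see above". Under Missing Items on Questionnaire Scales, the subscores, ending with "nocturnal stools and activity level are scored as a 2 day average, rounded to one decimal place", are rounded singly and the total is not. The Rounding paragraph of SAP 6.0 then states: "No rounding will be performed before or during analyses/calculations".

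Two endpoints use the total: "PUCAI remission is defined as PUCAI < 10" and "PUCAI response is defined as a decrease in PUCAI ≥ 20 points from Study M11-290-Baseline". SAP 7.1 says that for marked items "the source data from Study M11-290 should be used for analyses", and one of those items is "PUCAI at Study M11-290-Baseline". Neither document says how that parent-study value was rounded.

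**Height.** SAP 10.2 lists change from Baseline in z for height, next to change in z for weight-for-age. Protocol 5.3.2 also names a z score for height. The only formula, in SAP 6.0 (Score Definitions, Other), is labelled as a z score for height velocity and works in cm/yr. The same paragraph takes the mean and SD from the CDC stature-for-age file. Protocol 5.3.1.1 (Anthropometric Evaluations) prints the same velocity formula but calls the result the z score for height.

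**The concern.** For PUCAI, the same diary entries can give a different remission status depending on which document is followed. The SAP does more than omit the round-up: its general rounding rule bars a programmer from applying it. SAP 12.0 declares no changes, so the difference is not presented as a deliberate departure from the protocol.

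For height, the formula and its reference table measure different things. Subtracting a mean stature in cm from a velocity in cm/yr does not give a z score, and no source of mean velocities is named. Whoever programs the endpoint must set aside part of the written plan and decide which part.

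Both derivations feed listed efficacy endpoints. SAP 10.1 rules out confirmatory testing, so reported proportions and growth summaries are at stake, not a test result.

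**Working it through.** **Check of the scale.** The item maxima in SAP 6.0 and Protocol Appendix C sum to 10 + 30 + 10 + 15 + 10 + 10 = 85, the stated maximum.

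**Attainable scores.** Daily totals take all 18 multiples of 5 from 0 to 85. Their two-day averages, and equally the sums of two-day subscore averages, lie on a 2.5-point grid: 85/2.5 + 1 = 35 values. Rounding subscores to one decimal changes nothing on this grid.

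**Remission.** Let r(x) = 5 × ceil(x/5) be the protocol's round-up. Compare x < 10 (SAP) with r(x) < 10 (protocol):

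| Two-day score x | r(x) | SAP | Protocol |
|---|---|---|---|
| 0 | 0 | remission | remission |
| 2.5 | 5 | remission | remission |
| 5 | 5 | remission | remission |
| 7.5 | 10 | remission | not remission |
| 10 or more | 10 or more | not remission | not remission |

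Only 7.5 changes. It arises from daily totals of 0 and 15, or of 5 and 10, in either order.

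**Weight of one subject.** SAP 4.3 expects 55 subjects outside Japan: 1/55 = 1.8 percentage points. With fewer subjects observed at later visits (assumed numbers), 1/40 = 2.5 and 1/20 = 5.0 points. For scale, the 95% CI half-width at n = 55 and an assumed 50% rate is 1.96 × sqrt(0.25/55) = 13.2 points.

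**Response.** Let b be the Study M11-290 Baseline and v the visit score. The SAP rule is b − v ≥ 20. Applying the protocol's round-up gives three cases. Cases (a) and (b) assume that the parent Baseline is also a two-day average on the 2.5 grid.

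- (a) Both rounded, r(b) − r(v) ≥ 20: response is gained when the unrounded drop is 17.5 and b is a half-step, from (17.5, 0) and (22.5, 5) to (82.5, 65). That is (82.5 − 17.5)/5 + 1 = 14 pairs gained, 0 lost.
- (b) Only the visit rounded, b − r(v) ≥ 20: response is lost when the drop is exactly 20 and v is a half-step, from (22.5, 2.5) to (82.5, 62.5). That is (62.5 − 2.5)/5 + 1 = 13 pairs lost, 0 gained.
- (c) b already a multiple of 5: 18 × 35 = 630 pairs, none of which changes.

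These are counts of possible score pairs, not of subjects.

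**Height.** Illustration only, with every input assumed: velocity 0 to 10 cm/yr, mean stature 100 to 175 cm, SD 5 to 8 cm.

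- With the difference bracketed, (velocity − mean)/SD runs from (0 − 175)/5 = −35.0 to (10 − 100)/8 = −11.25.
- As printed, without those brackets, velocity − mean/SD runs from 0 − 175/5 = −35.0 to 10 − 100/8 = −2.5, and still mixes units.

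Neither form is a usable z score.

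**The case against.** The strongest reply on PUCAI is that the protocol (Section 8.1) leaves analysis detail to the SAP, and the SAP gives one rule, so a programmer faces no real ambiguity. The SAP is also based on Amendment 3 and the protocol supplied is Amendment 5, so the stale text cannot be identified with certainty. This stands in part. Version lag is possible, and the Amendment 5 list of changes does not mention PUCAI scoring. The current texts still disagree on an endpoint that both define with the same cut-off, and the SAP declares no departure.

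The size is small and may be nil: one score in 35, an unknown number of subjects, descriptive analyses only. That stands and limits the weight of the point. It also stands that the response cases depend on an unseen parent-study rule, and that SAP 7.1's source-data instruction is written for baseline summaries. Its extension to the response endpoint is an inference. This is a reason to state the Baseline rule.

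On height, SAP 6.0 cites the CDC page for derivation details, and the endpoint name, the table and the weight-for-age endpoint all point to height-for-age. The intent is probably recoverable. The written formula nevertheless remains, and it contradicts that intent. The numerical range above rests on assumed extremes, and its upper end depends on brackets that are not printed, so it is no more than an illustration.

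Finally, changing the SAP's height formula moves it away from the Protocol 5.3.1.1 wording until the protocol is amended. That is a fair cost, and the departure should be stated.

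**Conclusion.** Both rules are wrong as written and should be corrected.

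- **PUCAI remission:** the SAP is more lenient than the protocol at exactly one score, 7.5, and never stricter. The effect is 1.8 points per affected subject at n = 55, with an unknown and possibly zero number affected.
- **PUCAI response:** the documents do not fix the direction. The round-up can add responders, remove them or change nothing, depending on the unstated rounding of the Study M11-290 Baseline.
- **Height:** the formula with the named table gives no valid z. This follows from the mismatch of quantities and does not depend on the assumed values in the illustration.

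The missing brackets in the height formula are a minor point.

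**What to change.** **PUCAI (SAP 6.0).** Keep the two-day subscore averages and the subscore carry-forward. Then round the summed total up to the next multiple of 5 before applying the remission and response cut-offs, as a stated exception to the no-rounding rule. State how the Study M11-290 Baseline is rounded, and use the same rounding for Baseline and visits when deriving response. If that Baseline differs from the value reported in Study M11-290, say so in a footnote.

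**Height (SAP 6.0).** Replace the velocity formula with height-for-age z: observed height against the named stature-for-age reference, by age and sex. State that this departs from the formula in Protocol 5.3.1.1, and align that wording at the next amendment. Only if velocity is truly intended, rename the endpoint, name a velocity reference, correct the brackets and define the measurement interval. Planned heights are 24 or 48 weeks apart (0.46 or 0.92 years), and a Baseline velocity needs an earlier height from Study M11-290.

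**Cost.** SAP wording and two derivations, with no new data. PUCAI remission may fall slightly; with matched rounding, response may rise slightly or stay the same. The Baseline used for response may differ from the parent-study report, hence the footnote.

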3. IMPACT III

The IMPACT III questionnaire assesses quality of life in IBD related fields and comprises 35 closed questions with a 5-point Likert scale for all answers ('good'

through 'bad' answers scored by 5 through 1; range of total score 35 - 175, higher scores suggesting higher quality of life).

Total Score: sum of Q1 - Q35

Subscores:

• Bowel symptoms (7 items: Q1, Q3, Q10, Q19, Q21, Q25, Q31)

• Systemic symptoms (3 items: Q6, Q28, Q32)

• Emotional functioning (7 items: Q4, Q5, Q11, Q12, Q13, Q16, Q29)

Social functioning (12 items: Q8, Q9, Q14, Q17, Q18, Q20, Q23, Q26, Q27, Q30, Q34, Q35)

• Body image (3 items: Q7, Q15, Q33)

• Treatment/interventions (3 items: Q2, Q22, Q24)

4. WPAI

The WPAI was developed to measure the effect of disease on productivity at work and its impact on daily activities. The questions ask about the impact of disease to the patient's caregiver within the past 7 days. Six questions asked on this questionnaire can be described briefly as follows:

Questions:

- Q1. Currently employed (working for pay)? (Yes/No)
- Q2. Hours missed from work due to PROBLEM.
- Q3. Hours missed due to other reasons.
- Q4. Hours actually worked.
- Q5. Degree PROBLEM affected productivity while working.
- Q6. Degree PROBLEM affected regular activities other than job.

WPAI scores are expressed as *percent impairment* based on the above questions. The four main impairment measures or scores are derived as follows:

Scores:

S1. *Absenteeism*: Percent work time missed due to PROBLEM:

$$100 \times \left[\frac{Q2}{O2 + O4} \right]$$

S2. **Presenteeism**: Percent impairment while working due to PROBLEM: $100 \times \left[\frac{Q5}{10} \right]$

S3. Percent *overall work impairment* due to PROBLEM:

$$100 \times \left[\frac{Q2}{Q2 + Q4} + \left\{ 1 - \frac{Q2}{Q2 + Q4} \right\} \times \frac{Q5}{10} \right]$$

S4. Percent *activity impairment* due to PROBLEM: $100 \times \left[\frac{Q6}{10} \right]$

5. Other

Body Mass Index (BMI, in kg/m²) will be obtained as:

 $BMI = weight (kg)/(height [m] \times height [m])$

"z" score for height velocity will be obtained as: (Observed height velocity [cm/yr] – mean height velocity for age and sex [cm/yr]/[SD of the mean]). NOTE: The mean and Standard Deviation (SD) will come from published table values: The CDC Growth Charts webpage of the Center for Disease Control and Prevention with derivation details on the "z" score:

[figure not shown]
http://www.cdc.gov/growthcharts/percentile_data_files.htm, STATAGE.xls ('stature-for-age-chart,' for height) to be used.

Inappropriate Tanner stage will be defined depending on age and sex as follows: $girls \ge 14$ years/boys ≥ 15 of age with a Tanner stage of 1; $girls \ge 16$ years/boys ≥ 18 of age with a Tanner stage < 4; $girls \ge 19$ years/boys ≥ 19 of age with a Tanner stage of < 5.1.

7.0 Demographics, Baseline Characteristics, Medical History, and Previous/Concomitant Medications

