Subjects who have been in remission (PMS \leq 2 with no individual subscore > 1) for at least 8 weeks and for at least 2 consecutive visits may have their dosage de-escalated from ew to eow prior to Amendment 4 or to the next lower dose after Amendment 4. The investigator should receive prior approval from the medical monitor before taking any action with regard to dose de-escalation.

Subjects who demonstrate disease flare after dose de-escalation have an opportunity to re escalate their dose back to adalimumab ew dosing prior to Amendment 4 or to the next higher dose after Amendment 4. The investigator should receive prior approval from the medical monitor before taking any action with regard to dose re-escalation. One de-escalation within a period of 48 weeks and one re-escalation within a period of 48 weeks are permissible.

Methodology (Continued):

UC-related concomitant medication:

- Subjects who enroll into the study from blinded treatment in Study M11-290 will be allowed to change/initiate/discontinue their steroid dose after 4 weeks in Study M10-870.
- Subjects who enroll into the study from blinded treatment in Study M11-290 will be allowed to change/initiate/discontinue their azathioprine, 6-MP, MTX, 5-ASA doses after 8 weeks in Study M10-870.
- Subjects who enroll into the study from open label treatment in Study M11-290 will be allowed to change/initiate/discontinue their azathioprine, 6-MP, MTX, 5-ASA at any time point in Study M10-870.
- Reductions in concomitant corticosteroids, azathioprine, 6-MP, MTX, and 5-ASA will be allowed at any time in the event of moderate or severe drug-related toxicities (e.g., leukopenia, anemia, neuropathy).

The duration of the study could last up to 298 weeks (approximately 5.5 years). Subjects who complete, or who early terminate from the study will be contacted approximately 70 days after their last dose of study drug to obtain information on any ongoing and new adverse events (AEs). At study visits in addition to routine physical examination, laboratory assessments and calculation of the PMS and PUCAI, the following will be collected:

- Anthropometric evaluations at for determination of body mass index (BMI), and "z" scores for height and weight.
- IMPACT III Quality of Life questionnaire will be completed for subjects 9 years of age or older
- WPAI
- Tanner stage

This study will conclude approximately 12 weeks after one of the following criteria have been satisfied:

[figure not shown]

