An x-ray of the wrist for the assessment of bone age will be obtained at Baseline; Weeks 48, 96, 144, 192, 240 and 288 visit to determine changes in bone maturation. Sites should use the Greulich and Pyle method for reading the x-ray.²¹ The x-ray report requires the signature of the radiologist who read the films. The bone age that is determined by the x-ray should be recorded on the eCRF. Assessment of bone age will not be required for subjects at the Premature Discontinuation visit.

The x-ray collected at the Week 52 visit of Study M11-290 will be used for the Baseline assessment (prior to receiving study drug). If the height velocity is 0 and, in the opinion of the investigator, a subject is no longer growing, the x-ray for bone age can be omitted.

[figure not shown]
Anthropometric Evaluations

Height and weight obtained at Baseline, Weeks 24, 48, 72 and 96, 144, 192, 240 and 288/Premature Discontinuation will be used by AbbVie Data Management and Statistical groups for determination of BMI and "z" score (observed height velocity [cm/yr] – mean height velocity for age and sex [cm/yr]/SD of the mean) for height.

At Baseline, height from the Week 52 visit of Study M11-290 will be used and maximal weight attained will be recorded.

Tanner Stage

Tanner Stage will be assessed at Baseline, Weeks 48, 96, 144, 192, 240 and 288/Premature Discontinuation Visit. Tanner Staging should be captured on the appropriate eCRF page. The Tanner Stage assessed at the Week 52 visit of Study M11-290 will be used for the Baseline assessment (prior to receiving study drug).

Pediatric Ulcerative Colitis Activity Index (PUCAI)

A PUCAI score will also be calculated at all study visits beginning at Baseline. The PUCAI score calculated at the Week 52 visit of Study M11-290 will be used for the Baseline assessment (prior to receiving study drug).

An example of the PUCAI is located in Appendix C.

[figure not shown]

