5.3.2 Efficacy Variables

This study will utilize the PMS (and Mayo score if available) and PUCAI to determine efficacy of the study drug.

The following efficacy endpoints will be analyzed using summary statistics:

- The proportion of subjects who achieve clinical remission as measured by PMS (defined as a PMS ≤ 2 and no individual subscore ≥ 1) over time;
- The proportion of subjects who achieve clinical response as measured by PMS (defined as a decrease in PMS ≥ 2 points and ≥ 30% from Study M11-290 Baseline) over time;
- The proportion of subjects who achieve PUCAI remission (defined as < 10) over time;
- The proportion of subjects who achieve PUCAI response (defined as a decrease in PUCAI ≥ 20 points from Study M11-290 Baseline).

Efficacy will also be evaluated based on other measures of disease activity, including IMPACT III, WPAI, z-score for height and weight, bone age, BMI, and laboratory values as applicable. The proportion of subjects who achieve remission/response based on Mayo score and mucosal healing based on Mayo endoscopy subscore will be summarized for subjects with available Mayo score.

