10.2 Efficacy Analysis

The efficacy endpoints are:

- The proportion of subjects who achieve clinical remission as measured by PMS (defined as a PMS ≤ 2 and no individual subscore ≥ 1) over time;
- The proportion of subjects who achieve clinical response as measured by PMS (defined as a decrease in PMS ≥ 2 points and ≥ 30% from Study M11-290-Baseline) over time;
- The proportion of subjects who achieve PUCAI remission (defined as < 10) over time;
- The proportion of subjects who achieve PUCAI response (defined as a decrease in PUCAI ≥ 20 points from Study M11-290-Baseline).
- Change from Baseline in total IMPACT III Quality of Life score and subscores over time for subjects at least 9 years old at Baseline;
- Change from Baseline in WPAI scores over time;
- Change from Baseline in "z" scores for height over time;
- Change from Baseline in BMI over time;
- Change from Baseline in "z" scores for weight-for-age over time;
- Change from Baseline in albumin and total protein over time;
- Change from Baseline in hemoglobin, hematocrit, red blood cell count over time;
- Change from Baseline in hs-CRP levels over time;
- Proportion of subjects at appropriate Tanner stage (see Section 6.0) over time;
- Proportion of subjects in Mayo score clinical response over time (for subjects with available Mayo score);
- Proportion of subjects in Mayo score clinical remission over time (for subjects with available Mayo score);
- Proportion of subjects who achieve mucosal healing over time as measured by Mayo endoscopy subscore (defined as ≤ 1, for subjects with available Mayo score)
- Proportion of subjects in 9 point Mayo score (without PGA) clinical remission over time (for subjects with available Mayo score);

• Proportion of subjects in 6 point Mayo score (without PGA and endoscopy subscore) clinical remission over time (for subjects with available Mayo score).

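### The height z-score combines a height-velocity formula, a stature-for-age reference file and a height endpoint, and the three cannot all be followed

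*SAP*

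**What the plan says.** **SAP Section 6.0, Score Definitions, Other.** The score is introduced as one for height velocity and written as "Observed height velocity [cm/yr] – mean height velocity for age and sex [cm/yr]/[SD of the mean". The text then says that the mean and SD come from published tables on the CDC growth-chart page, points to that page for the z-score derivation, and ends with "STATAGE.xls ('stature-for-age-chart,' for height) to be used".

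**SAP Section 10.2.** The listed endpoint is "Change from Baseline in 'z' scores for height over time". There is no height-velocity endpoint in the list, and the SAP gives no other formula for a height z-score.

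**Protocol Section 5.3.1.1, Anthropometric Evaluations.** The same velocity expression appears, but the result is called a z-score for height: "mean height velocity for age and sex [cm/yr]/SD of the mean) for height". Heights are scheduled at Baseline, Weeks 24, 48, 72 and 96, and then Weeks 144, 192, 240 and 288. For the starting value, "At Baseline, height from the Week 52 visit of Study M11-290 will be used".

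**Protocol Section 5.3.2.** The efficacy variable is again height: "z-score for height and weight, bone age, BMI, and laboratory values as applicable". The protocol synopsis also names z-scores for height and weight.

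**The concern.** A z-score compares an observed value with the mean and SD of the same quantity in a reference population. Here the observed value is a growth rate in cm/yr, the reference describes attained height in cm, and the endpoint is named as height. Reference and endpoint agree with each other; the formula agrees with neither.

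The SAP exists to direct programming, and on this endpoint the programmer has to override part of it. Height-for-age and height velocity are different measures, so the choice determines what is reported as the change from Baseline, with its 95% confidence interval (SAP Section 10.1). Growth matters in this population: protocol Section 3.2 treats freedom from adverse effects on linear growth as a requirement of therapy in pediatric UC.

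Two smaller faults lie in the same line. As bracketed, only the mean is divided by the SD. And an SD described as being of the mean is not, read literally, the reference-population SD.

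**Working it through.** The documents give no numerical value for this score, so there is no figure to reproduce. **All velocities, means and SDs below are assumptions**, used only to show size.

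**1. Stature reference put into the velocity formula.** Take velocity 6 cm/yr, mean stature 150 cm, SD 7 cm.
- Whole difference divided by the SD: (6 − 150)/7 = −20.6.
- As bracketed: 6 − 150/7 = −15.4.

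Range over velocities 0 to 10 cm/yr, means 110 to 176 cm and SDs 5 to 7.5 cm:

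| Reading | Nearest to zero | Furthest from zero |
|---|---|---|
| Whole difference divided | (10 − 110)/7.5 = −13.3 | (0 − 176)/5 = −35.2 |
| As bracketed | 10 − 110/7.5 = −4.7 | 0 − 176/5 = −35.2 |

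Zero velocity is a case the protocol itself foresees, under Bone Age: "If the height velocity is 0 and, in the opinion of the investigator, a subject is no longer growing".

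**2. Does change from Baseline cancel the error?** Take a child always exactly at the assumed mean height, so that the true height-for-age z is 0 throughout and its change is 0. Start at velocity 6, mean 140, SD 7.

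| Later visit | Whole difference divided | As bracketed |
|---|---|---|
| Velocity 6, mean 152, SD 7.5 | (6 − 152)/7.5 − (6 − 140)/7 = −0.3 | (6 − 152/7.5) − (6 − 140/7) = −0.3 |
| Velocity 0, mean 163, SD 6.5 | (0 − 163)/6.5 − (6 − 140)/7 = −5.9 | (0 − 163/6.5) − (6 − 140/7) = −11.1 |

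The error nearly cancels while growth is steady, but not when growth stops. Subjects aged 4 to 17 (protocol Section 3.3.1) may be followed for up to 298 weeks, so some can be expected to stop growing on study.

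**3. Could velocity be meant, with a proper reference?** Assume a velocity mean of 6 and SD of 1.5 cm/yr.
- Child growing at 5 cm/yr: (5 − 6)/1.5 = −0.67; as bracketed, 5 − 6/1.5 = +1.0.
- Child growing exactly at the mean: (6 − 6)/1.5 = 0; as bracketed, 6 − 6/1.5 = +2.0.

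The first child, if currently 140 cm tall against a mean of 140 cm, has a height-for-age z of (140 − 140)/7 = 0 but a velocity z of −0.67. The two repairs do not report the same thing.

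**4. Can the named file supply the velocity reference?** Differences between age-specific mean statures could approximate a mean velocity. The velocity SD, however, depends on the within-child correlation r between ages: SD = √(s₁² + s₂² − 2·r·s₁·s₂). With assumed SDs of 6.5 and 7.0 cm one year apart, r = 0.90 gives 3.06 cm/yr and r = 0.99 gives 1.08 cm/yr. The documents give no correlation.

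**5. Interval and Baseline.** A velocity needs two heights and a stated interval. The protocol schedule spaces heights 24 weeks apart to Week 96 and 48 weeks apart afterwards, with no rule for forming a rate. SAP Section 11.4, by contrast, lists height among measurements taken at every visit, which leaves the interval less defined still. One Baseline height gives no Baseline velocity, so change from Baseline has no starting value unless an earlier parent-study height is specified.

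**The case against.** The best defence is that the ambiguity is small in practice. The SAP closes with an instruction to use a height file, points to that source's own z-score derivation, and lists only a height endpoint. The velocity line looks like leftover text. A competent programmer would compute height-for-age and would reject a score of −20 on sight, so the extreme values above are not a likely published error. This is fair, and it is why height-for-age is the preferred repair. But it means departing from a formula written in both documents, a choice that the SAP should make and record.

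The wording of the SD is largely answered by the SAP's next sentence, which takes it from published tables. The misplaced bracket is secondary too: few would code it literally, though it appears in both documents.

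The Baseline-velocity problem matters only if velocity was intended. The protocol does not forbid earlier heights, and SAP Section 7.1 already draws Baseline height from parent-study data. Whether still earlier heights exist cannot be judged from these two documents.

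Finally, this is one of 18 listed efficacy endpoints, all descriptive. That limits the consequence but does not remove the contradiction.

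**Conclusion.** The concern holds. Formula, reference and endpoint are mutually incompatible in the current text, and nothing elsewhere in either document resolves them. Following the formula with the named file gives a meaningless score, −13.3 to −35.2 over the assumed grid when the whole difference is divided by the SD. Change from Baseline can then be wrong by several units (−5.9 in the example where growth stops, against a true change of 0). These sizes rest entirely on assumed reference values; the incompatibility itself does not.

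The point should be fixed before analysis. It affects one descriptive growth endpoint and has no bearing on sample size or on any confirmatory test, since none is planned.

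**What to change.** Make variable, formula and reference agree in SAP Sections 6.0 and 10.2 and in protocol Section 5.3.1.1.

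- **Preferred:** replace the velocity formula with the height-for-age z-score for exact age and sex, derived from the named stature-for-age reference by that source's own method. The endpoint name can stay. Height, age and sex are already collected, so the cost is wording only.
- **If velocity is intended:** rename the endpoint, name a height-velocity reference by age and sex, define the interval between heights and how Baseline velocity is obtained, and write the score as (observed − mean)/reference SD. This also needs an earlier parent-study height for each subject.

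The same edit could supply a formula and reference file for the weight-for-age z-score in SAP Section 10.2, for which Section 6.0 states neither.
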